13.7 Blinding and Unblinding Procedures

13.7.1 Blinding

The IDMRS staff is responsible for maintaining security of the treatment assignments. The subject, the clinical staff, and the study team will be blinded to treatment allocation. The study arm agents will be ordered according to the randomization code list maintained by the IDMRS in the electronic Investigational Drug Management System (IDMS).

13.7.2 Unblinding

13.7.2.1 Scheduled Unblinding

Unblinding will occur for every participant at the end of the 24-week period in Part I after the laboratory analysis for the primary endpoints (NKG2D and EBV by FISH) has been completed. At this point, participants will be informed about their treatment assignment in Part I.

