3.2 Study Endpoints

Primary Endpoints

- Cohort 1: Difference between the absolute number of EBV-infected B cells (by EBV FISH) after 12 weeks of oral magnesium supplementation and after 12 weeks of placebo.
- Cohort 2: Difference between NKG2D expression in CD8 T cells after 12 weeks of oral magnesium supplementation and after 12 weeks of placebo.

Secondary Endpoints

- Incidence and severity of AEs throughout the study.
- Contingent upon patient participation in Part II, differences in EBV viral load and number (or percent) of EBV-infected B cells (cohort 1) or NKG2D expression in CD8 T cells (cohort 2) by duration (12 weeks of IV+oral versus 24 weeks of IV+oral) of magnesium supplementation regimen.
- Change in the intracellular pool of free Mg²⁺ by duration of magnesium supplementation regimen.
- Change in NKG2D expression in cohorts 1 and 2.

Exploratory Endpoints

- Change in CD4 T cell counts, B cell counts (or percent), and/or in NKG2D expression on NK (CD3-CD56+) cells.
- Quantification of EBV-infected B cells as determined by flow cytometry and FISH.
- Percent of anemia, neutropenia, thrombocytopenia, and abnormal liver enzymes.
- Difference in number and severity of infections between placebo and magnesium treatment periods.
- Difference in number of health-related days of missed school/work between placebo and magnesium treatment periods.
- Difference in number of emergency room visits and hospital admissions between placebo and magnesium treatment periods.

4 Study Population

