10.3 Investigator Assessment of Adverse Events

If a diagnosis is clinically evident (or subsequently determined), the diagnosis rather than the individual signs and symptoms or lab abnormalities will be recorded as the AE.

All AEs thought to be related to magnesium therapy or study procedures occurring from the time the informed consent is signed through the final study visit will be documented, recorded, and reported.

The Investigator will evaluate all AEs with respect to **Seriousness** (criteria listed above), **Severity** (intensity or grade), and **Causality** (relationship to study agent and relationship to research) according to the following guidelines.

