10.3.2 Causality

Causality (likelihood that the event is related to the study agent) will be assessed considering the factors listed under the following categories:

Definitely Related

- reasonable temporal relationship
- follows a known response pattern
- clear evidence to suggest a causal relationship
- there is no alternative etiology

Probably Related

- reasonable temporal relationship
- follows a suspected response pattern (based on similar agents)
- no evidence of a more likely alternative etiology

Possibly Related

- reasonable temporal relationship
- little evidence for a more likely alternative etiology

Unlikely Related

- does not have a reasonable temporal relationship
OR
- good evidence for a more likely alternative etiology

Not Related

- does not have a temporal relationship
OR
- definitely due to an alternative etiology

Note: Other factors (e.g., dechallenge, rechallenge) should also be considered for each causality category when appropriate. Causality assessment is based on

available information at the time of the assessment of the AE. The investigator may revise the causality assessment as additional information becomes available.

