To determine which participants will continue to Part II, we will evaluate the MFI for NKG2D in CD8+ T cells in each patient after 12 weeks of oral magnesium and after 12 week of placebo. If a patient has a 2-fold or greater increase with oral magnesium as compared with placebo, then that patient's study participation will end. Those patients who do not meet this outcome will proceed to Part II (IV magnesium). Participation in Part II will depend on the result for each individual patient.

Contingent upon patient participation in Part II, secondary analysis will compare the MFI for NKG2D on CD8+ T cells at the end of 12 weeks versus 24 weeks of oral supplementation.

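### A participant's code can be released before that participant's adverse-event grades, causality calls and infection data from Part I are final

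*Combined protocol and SAP*

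**What the plan says.** Under 13.7.1, "The subject, the clinical staff, and the study team will be blinded to treatment allocation". Section 13.7.2.1 ends this one participant at a time: "Unblinding will occur for every participant at the end of the 24-week period in Part I", subject to a single condition, "after the laboratory analysis for the primary endpoints (NKG2D and EBV by FISH) has been completed". It continues: "At this point, participants will be informed about their treatment assignment in Part I". The break is individual because each participant's magnesium and placebo results decide the next step. Section 13.2 puts it as "Participation in Part II will depend on the result for each individual patient".

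On adverse events, 10.3 states that "All AEs thought to be related to magnesium therapy or study procedures" arising between consent and the final visit are to be documented, recorded and reported. Section 10.1 sends every event to a source document but only reportable AEs to CRIMSON, with severity and the principal investigator's view of relatedness. Section 10.3.2 adds: "The investigator may revise the causality assessment as additional information becomes available". Section 10.5 keeps AEs under follow-up until they resolve or the study ends.

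Among the endpoints in 3.2, AE incidence and severity is secondary. An exploratory endpoint is "Difference in number and severity of infections between placebo and magnesium treatment periods".

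**The concern.** In a two-period crossover, one code break labels every Part I event of that participant as belonging to magnesium or to placebo. Any item that rests on judgement and is settled or changed afterwards is no longer a blinded assessment, although Part I is described as double-blind. The unblinding rule protects the two primary assays from this and is silent on the rest.

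At stake is the credibility of those Part I safety and infection results that depend on an assessor's judgement. An investigator who knows that an event fell in a placebo period may find it harder to call it magnesium-related, and may grade a borderline infection differently. This concerns the unblinded participant's own data. It is separate from whether released codes help anyone guess later participants' sequences.

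**Working it through.** The plan gives no figure on this point, and its power statement does not enter. The check is a comparison of sections.

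**1. What the release condition covers.** The Part I outcomes, set against 13.7.2.1:

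| Part I outcome | Covered? | Open to judgement? | Stated magnesium–placebo contrast? |
|---|---|---|---|
| NKG2D on CD8 T cells, EBV FISH (primary) | Yes | Assessor blinded (3.1) | Yes |
| AE grade and causality (secondary) | No | Yes; causality revision expressly allowed (10.3.2) | No; the endpoint is AEs throughout the study |
| Infection number and severity (exploratory) | No | Yes, above all severity | Yes |
| Missed days, emergency visits, admissions (exploratory) | No | Little; these are counts | Yes |
| Intracellular free Mg²⁺ (secondary) | No | Laboratory readout | No; the endpoint is change by duration of regimen |

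The second and third rows are both uncovered and judgement-based. They carry the point.

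**2. Whether another section closes the gap.** Sections 10.1 and 15.1 ask for timely review and recording. Neither requires sign-off or a lock before the code is released. Section 12.1 limits site monitoring to pediatric subjects, so that check on AE data does not reach adults. The only assessor named individually as blinded (3.1) is the one measuring the primary assays.

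**3. When the exposure arises.** AEs are elicited before and one week after each dose escalation and at the visits in Weeks 4, 8, 12, 16, 20 and 24 (6.3, 10.1). Infections are asked about at each visit, back to the previous one (section 7). Collection for Part I is therefore finished by Week 24, while blinded. What remains is entry, grading or revision after the code break. It bears mainly on events near Week 24 and on AEs still open then, which 10.5 keeps under assessment.

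**4. Whether the assessor knows the order by then.** Section 13.7.2.1 says only that participants are told. The rule for entering Part II compares magnesium with placebo within each participant, so someone applying it must know the order, and participants can tell staff. That the team knows is a strong inference, not a stated fact.

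**5. How a causality call can reach the data.** Section 10.3 ties recording to perceived relatedness, and 10.1 ties CRIMSON entry to reportability. A call made late and unblinded can therefore influence whether an event is entered, and how it is attributed.

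**6. Size.** An estimate would need the AE rate per period, the share of items still open at code release, and the probability and direction of a changed call. The documents give none of these.

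**The case against.** The strongest reply is that the gap is narrow, and much of that reply stands.

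- The secondary AE endpoint names neither relatedness nor a contrast between periods, and it also covers open-label Part II. Section 13 plans no AE test between periods. The AE summary is affected only if it is split by period.
- All events reach a source document (10.1), and 10.4.3 reports AEs annually apart from waived expected ones. Nothing says that an AE already in CRIMSON is removed when its causality is revised.
- Most judgements are made while blinded. Related SAEs go to the IRB within 7 calendar days (10.4.1), and events that pause a subject within one business day (10.7.1).
- Individual unblinding is inherent in the Part II rule and follows completion of the primary assays.

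A reader might infer more than this supports. One stronger reading is that all secondary and exploratory outcomes are compromised. The table above does not bear that out: missed days and visits are counts, and free Mg²⁺ is a laboratory measurement whose endpoint is by duration. Another puts a number on the bias. With 20 patients and an assumed 30% AE rate in each period, 20 × 0.30 = 6 events per period; if half the placebo events were later judged unrelated and dropped, 6 v 6 would become 6 v 3, an apparent doubling. The rate and the half are both assumed, the revision runs one way only, and the result needs recorded events to be deleted, which no section provides for.

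The reply does not supply a rule that settles the judgement-based items before the code is released. That part of the concern remains.

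**Conclusion.** The point holds in a limited form. The plan allows a participant's Part I AE grades and causality and infection data to be entered, graded or revised after that participant's treatment order is known. Revision is expressly permitted only for causality; for grade and infection data the exposure follows from the absence of any completion rule. It bears on the exploratory infection comparison and on the AE summary if presented by period. The primary tests are untouched, and Part II, being open label, is made no worse.

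The size of the bias is unknown: zero if nothing is settled late, and otherwise not estimable from the documents. The conclusion assumes that whoever assesses AEs learns the order at code release. The change is worth making because it is cheap and extends to these items the protection already given to the primary assays.

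**What to change.** Amend 13.7.2.1 so that a participant's code is released only when both conditions are met:

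1. The laboratory analysis of the primary assays is complete.
2. That participant's AE terms, grades and causality, and the number and severity of infections, through Week 24 are entered and signed off in CRIMSON.

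Add that later changes remain allowed for safety follow-up but are audit-trailed and flagged as made after unblinding. Part I comparisons between periods use the blinded assessments, and a sensitivity analysis includes the later corrections. Legitimate updates, such as a new diagnosis for an AE open at Week 24, are then neither lost nor mixed unmarked with blinded calls. Free Mg²⁺ should not be made a condition: its assay turnaround is not stated, and waiting for it could delay the Part II decision.

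The cost is prompt data entry and sign-off for each participant and a short delay before code release. Sign-off can proceed while the primary assays are being read, and should fit within the washout of at least 2 weeks before Part II (6.4.1). It needs no extra visit or sample.

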13.7.2.2 Unscheduled Unblinding

Intentional: Any subject that is unable or unwilling to complete the 24-week period will be taken off study and unblinding will occur. To break a treatment blind, the PI, after consulting with the medical advisory investigator, will request a subject's treatment assignment from the IDMRS. If an emergency request for treatment assignment is made by an individual other than the PI and the PI is not immediately available, the request will be made to the medical advisory investigator or designee, as applicable, who will then contact the IDMRS or appropriate NIH Pharmacy after-hours contact to obtain the treatment assignment.

Unintentional: If unintentional unblinding of study treatment assignment occurs, the PI will create a plan for ongoing management of the subject(s) involved and preventing the recurrence of a similar incident, as appropriate. If the protocol team determines that the unintentional unblinding may have a significant impact on the study plan (e.g., if the treatment codes for multiple subjects or an entire cohort were accidentally broken), the need for a protocol amendment will be addressed as soon as possible.

Intentional and unintentional unscheduled unblinding will be documented in the appropriate source and/or research record and will include the reason for the unscheduled unblinding, the date it occurred, who approved the unblinding, who was unblinded, who was notified of the unblinding, and the plan for the subject. The PI will report all cases of intentional and unintentional unscheduled unblinding to the DSMB in writing within 1 business day after site awareness via email to the DSMB mailbox ([contact]) outlining the reason for the unblinding and the date it occurred. The report will also be submitted to the IRB.

If a serious adverse event (SAE) has resulted in unblinding, this information will be included in the SAE Report.

14 Ethics/Protection of Human Subjects

14.1 Informed Consent Process

Informed consent is a process where information is presented to enable persons to voluntarily decide whether or not to participate as a research subject. It is an ongoing conversation

between the human research subject and the researchers, which begins before consent is given and continues until the end of the subject's involvement in the research. Discussions about the research provide essential information about the study, including the purpose, duration, experimental procedures, alternatives, risks, and benefits. Subjects will be given the opportunity to ask questions and have those questions answered.

The subjects will sign the informed consent document prior to undergoing any research procedures. The subjects may withdraw consent at any time throughout the course of the trial. A copy of the informed consent document will be given to the subjects for their records. The researcher will document signing of the consent form in the subject's medical record. The rights and welfare of subjects will be protected by emphasizing to them that the quality of their medical care will not be adversely affected if they decline to participate in the study.

14.1.1 Non-English-Speaking Participants

If a non-English speaking participant is unexpectedly eligible for enrollment, the participant will be provided with the CC Short Written Consent Form for Non-English Speaking Research Participants in the participant's native language and a verbal explanation of the purpose, procedures and risks of the study as described in MAS Policy M77-2, NIH HRPP SOP 12 and 45 CFR 46.117(b)(2). The IRB-approved English consent form will serve as basis for the verbal explanation of the study. The investigator will obtain an interpreter unless the investigator is fluent in the prospective participant's language. Preferably, the interpreter will be someone who is independent of the participant (i.e., not a family member). Interpreters provided by the CC will be used whenever possible. The interpreters will translate the IRB-approved English consent form verbatim and facilitate discussion between the participant and investigator.

The IRB-approved English consent form will be signed by the investigator obtaining consent and a witness to the oral presentation. The CC Short Written Consent Form will be signed by the participant and a witness who observed the presentation of information. The interpreter may sign the consent document as the witness and, in this case, will note "Interpreter" under the signature line. A copy of both signed forms will be provided to the participant to take home.

The investigator obtaining consent will document the consent process in the participant's medical record (CRIMSON), including the name of the interpreter. Further, all instances of use of the CC Short Written Consent Form will be reported to the IRB at the time of annual review. If the CC Short Written Consent Form is used 3 times or more for the same language, this will be reported to the IRB immediately.

14.1.2 Telephone Consent Process

XMEN syndrome is rare and we will be required to recruit patients throughout the United States. We will obtain consent by telephone so that patients may begin the washout period at home and arrive at NIH ready to begin study participation.

- a) Permission to mail or fax the consent document will be obtained from the subject or the subject's legal guardian.
- b) Once consent is received, the subject is instructed to call the investigator for discussion of the study and consent document. The study will be thoroughly explained with ample time for

questions or concerns related to participation. Informed consent will be obtained by the principal investigator or a designated associate investigator on this protocol.

- c) The subject will identify him/herself by name and date of birth, and state that he/she gives consent to participate in this study. The staff member will verify the subject's name and the verbal consent to participate.
- d) Upon completion of the telephone call, the manner of obtaining consent and the names of the person administering and providing consent will be documented in the medical record, signed and dated.
- e) The subject/legal guardian must sign and date the consent in his/her possession and have the signature witnessed in-person and dated by an adult over the age of 18 years.
- f) This signed, witnessed, and dated consent must be sent to the investigator. No testing will occur without this consent.

Once received, the consent will be checked for accuracy and signed by the NIH investigator/designee. The signed consent will then be filed in the medical record.

14.1.3 Assent or Informed Consent Process (in Case of a Minor)

Assent forms will be used for all study participants between 7 and 18 years of age who are capable to give their assent to participate. Parental consent will be obtained for all study participants under the age of 18.

14.2 Subject Confidentiality

All records will be kept confidential to the extent provided by federal, state, and local law. The study monitors and other authorized representatives of the sponsor may inspect all documents and records required to be maintained by the Investigator, including, but not limited to, medical records. Records will be kept locked, and all computer entry and networking programs will be done with coded numbers only. Clinical information will not be released without written permission of the subject, except as necessary for monitoring by IRB, NIAID, the Office for Human Research Protections (OHRP), or the sponsor's designee.

15 Data Handling and Record Keeping

15.1 Data Capture and Management

Study data will be maintained in CRIMSON and collected directly from subjects during the study visits, or they will be abstracted from subjects' medical records. Source documents include all recordings of observations or notations of clinical activities and all reports and records necessary to confirm the data abstracted for this study. Data entry into CRIMSON will be performed by authorized individuals. The investigator is responsible for assuring that the data collected are complete, accurate, and recorded in a timely manner.

15.2 Record Retention

The investigator is responsible for retaining all essential documents listed in the ICH Good Clinical Practice Guideline. Study records will be maintained by the PI for a minimum of 3 years and in compliance with institutional, IRB, state, and federal medical records retention

requirements, whichever is longest. All stored records will be kept confidential to the extent required by federal, state, and local law.

Should the investigator wish to assign the study records to another party and/or move them to another location, the investigator will provide written notification of such intent to NIAID/OCRPRO with the name of the person who will accept responsibility for the transferred records and/or their new location. Destruction or relocation of research records will not proceed without written permission from NIAID/OCRPRO.

Appendix B: Schedule of Procedures/Evaluations

Evaluations	Blood volume (ml)	Enrollment ^a (begin 2-week washout)	Baseline visit	Part I (randomized crossover), Weeks 1-24				WASHOUT	Contingent upon each patient's outcome in Part I: Part II (open label), Weeks 27-50			
				Oral Mg L-threonate or placebo		Oral Mg L-threonate or placebo			Pre-infusion	IV MgSO ₄ (over 3 days of inpatient stay)	Oral Mg L-threonate escalation	
Study week (window)		Week -5 to Week -2	Day -3 to Day 0	Visits: Week 4 and 8 (+/-1 wk)	Week 12 evaluation (+/-1 wk)	Visits: Week 16, 20 (+/-1 wk)	Week 24 evaluation (+/-1 wk)	Week 25 ^b +26	Week 27 (+/-2 wks; inpatient stay of 4 to 6 days)	Week 38 (+/-2 wks)	Week 50 (+/-2 wks)	
Procedures												
Medical/medication history		X	X	X	X	X	X		X	X	X	X
Physical exam		X	X	X	X	X	X		X	X	X	X
IV magnesium										X		
EKG		X			X		X		X ^b	X ^b	X	X
CT ^c		X										
Oral supplement provision			X	X	X	X				X ^h	X	
Tolerance evaluation/dose escalation ^d				X		X						
Laboratory evaluations												
Urine spot Mg2+				X		X			X			
24-hr urine collection Mg2+			X		X		X			X ⁱ	X	X
CBC w/differential	3	X	X	X	X	X	X		X	X ^g	X	X
Acute care, mineral, hepatic panels	4	X	X	X	X	X	X		X	X ^g	X	X
Quantitative immunoglobins	4		X		X		X		X	X ^h	X	X
Lymphocyte phenotyping	6		X	X ^j	X	X ^j	X		X	X ^h	X	X
PT/PTT	4.5		X						X			
CMV PCR	3	X	X	X	X	X	X		X	X ^h	X	X
EBV PCR		X ^e	X	X	X	X	X		X	X ^h	X	X
HIV	8	X										
ESR	1		X	X	X	X	X		X	X ^h	X	X
CRP	4		X	X	X	X	X		X	X ^h	X	X
Total + ionized serum Mg ²⁺	1		X	X	X	X	X		X	X ^g	X	X
Research blood												
Intracellular free Mg ²⁺			X	X	X	X	X		X	X ^g	X	X
EBV FISH ^k		X	X ^e	X	X	X	X		X	X ^h	X	X
RNA extraction			X	X	X	X	X		X	X ^h	X	X
NKG2D expression			Xa	X	X	X	X		X	X ^g	X	X
Stored blood ^f	12		X	X	X	X	X		X	X ^h	X	X

Abbreviations: CBC=complete blood count, CMV=cytomegalovirus, CRP=C-reactive protein, CT=computed tomography, EBV=Epstein-Barr virus, EKG=electrocardiogram, ESR=erythrocyte sedimentation rate, FISH=fluorescent in situ hybridization, HIV=human immunodeficiency virus, IV=intravenous, MgSO₄=magnesium sulfate, NK=natural killer, PBMC=peripheral blood mononuclear cells, PCR=polymerase chain reaction, PT=prothrombin time, PTT=partial thromboplastin times, TBNK=T-lymphocyte, B-lymphocyte, and natural killer cells

Notes:

- a Evaluations may be conducted over 3 days.
- b EKG to be performed prior to infusion, 12, 24, and 48 hours after the start of the first infusion, and at completion of the infusion.
- c Low radiation CT scan to include neck, chest, abdomen, and pelvis if not done in the previous 3 months.
- d Patients will increase their dose of oral study agent every 2 weeks. Patients will be contacted prior to and 1 week after each dose escalation to assess for adverse events.
- e Blood will be drawn on 3 consecutive days to establish baseline values and to determine intrasubject variability.
- f Stored blood includes serum, plasma and PBMCs.
- g To be done 24 and 48 hours after starting and at completion of magnesium infusion.
- h Evaluations to be conducted upon completion of magnesium infusion.
- i 24-hour urine collection to begin 48 hours after initiation of magnesium infusion.
- j TBNK
- k EBV FISH will not be performed for EBV-naïve patients.

